3.4 Trial Treatment

The trial is an exposure to high oxygen (99%), delivered to the participant through a Health Canada approved (lic. #81363) face mask (supplied by Glenwood Labs Canada, Part #1041). The oxygen and room air are stored in high-pressure cylinders, which will be labelled with the investigational product name, study title, lot number and expiry date. The pressure is stepped down with Health Canada approved regulators, supplied by Western/Scott Fetzer Enterprise: WES M1-346-15FM for room air, and WES M1-540-15FM for high oxygen. The exposure to high oxygen and room air will both be for 2 min, and will occur on different experimental days.

3.5 Duration

The participant will be involved in four sessions of testing at a minimum of 2-week intervals between every testing session, each of which will take approximately 1.5 to 2 hours. A total duration of involvement in the study is a minimum of 7 weeks, with some possibly longer to fit in the 4 experiments according to participant and experimenter availability.

3.6 Discontinuation

Early signs of oxygen toxicity include acute tracheobronchitis, including a mild tickling sensation, later followed by inspirational pain, cough, and if more severe, a constant retrosternal burning sensation. If any of these symptoms are reported, we will immediately stop the delivery of high concentration of oxygen. Normally, these types of symptoms are not experienced until after 3 or more hours of exposure to high oxygen (Klein 1990).

3.7 Product Accountability

We will test oxygen exposure against room air (placebo).

3.8 Data Identification

The data will be recorded on RedCap with the assistance of the office of Quality Management for Clinical Research at the University of Alberta. RedCap data will include all relevant Case Report Forms, Informed Consent Forms, data from the von Frey hairs, and analyzed data from the reflexes.

4 Selection and Withdrawal of Subjects

4.1 Inclusion Criteria

SCI participants:

- i) traumatic SCI with onset ≥ 3 months prior,
- ii) between 18 - 65 yr old,
- iii) ASIA Impairment Scale at discharge classified as A, B or C,
- iv) injury level between C5 and T10,
- v) able to give informed, written consent.

Uninjured controls:

- i) no previous spinal cord injury or health condition that would confound the experiment or make it unsafe for the participant (see exclusion criteria),
- ii) between 18-65 yr old,
- iii) able to give informed, written consent.

4.2 Exclusion Criteria**SCI participants:**

- i) frequent uncontrolled autonomic dysreflexia,
- ii) uncontrolled high blood pressure,
- iii) cardiac or cardiovascular disease,
- iv) cancer,
- v) active urinary tract infection,
- vi) active pressure sores,
- vii) signs of deep vein thrombosis in the legs,
- viii) severe swelling of the feet and/or legs,
- ix) severe cognitive impairment,
- x) pulmonary dysfunction such as chronic obstructive pulmonary disease or acute respiratory infection,
- xi) any condition which would be exacerbated by sitting or lying in one position for 2 hours, such as low back pain,
- xii) pregnancy.

Uninjured controls:

- i) any active medical or neurological disorders,
- ii) cardiac or cardiovascular disease,
- iii) cancer,
- iv) signs of deep vein thrombosis in the legs,
- v) severe swelling of the feet and/or legs,
- vi) severe cognitive impairment,
- vii) pulmonary dysfunction such as chronic obstructive pulmonary disease or acute respiratory infection,
- viii) any condition which would make it difficult to remain sitting or lying in one position for over 2 hours, such as low back pain,
- ix) pregnancy.

4.3 Subject Withdrawal

Participants can withdraw at any time without consequence to them. They simply have to tell us they do not wish to continue. There will be no follow-up, and no consequence to the participants. There will be no need to replace participants, as this is not a clinical trial. We have factored in 10%-15% attrition.

4.4 Treatment of Subjects

During an experiment, participants will transfer to a wide, physical therapy plinth, and positioned in sitting, with the torso about 45 degrees from the vertical. The agent, high oxygen or room air, will be administered just once for a short duration. No other treatment is involved. On each testing day, participants will be exposed to one condition, either high oxygen or room air, and outcome measures will be taken before and after each exposure. On 2 of the testing days, the participants will be exposed to high oxygen, and on the other 2 days they will be exposed to room air. Testing sessions are spaced at least 2 weeks apart from each other.

4.5 Medication

As we have excluded all people with respiratory dysfunction, none of the participants will be on respiratory medications. We will document all other medications the participants are taking.

4.6 Monitoring for subject compliance

Not applicable. Participants will be in our lab the entire time.

5 Assessment of Efficacy

This is a one-time exposure to high oxygen during two experimental sessions. It is not meant to be efficacious as a treatment at this time. The experiment is a scientific study to determine how high oxygen, delivered for a short period, affects people with and without spinal cord injury. If exposure to high oxygen has a similar effect as it does in other animals with spinal cord injury, then new studies will be designed in the future to explore ways to improve oxygenation in people with spinal cord injury.

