PROTOCOL COVER PAGE

PROTOCOL NAME

Can brief exposure to hyperoxia improve function after chronic spinal cord injury?

PROTOCOL IDENTIFYING NUMBER

Pro00061817

PROTOCOL AMENDMENT VERSION

Version 13

PROTOCOL AMENDMENT DATE

October 1, 2021

GENERAL INFORMATION

Name and address of the sponsor and monitor of the study

University of Alberta, Edmonton, AB.

Name and address of the person authorized to sign the protocol and amendments

[name] [name], [name], University of Alberta

Name, title, address and telephone number(s) of the medical expert for the trial

[name], Associate Professor, Pulmonary Medicine, [name],
University of Alberta
[contact]

Name and title of the investigator(s) and sub-investigators responsible for the trial with address and phone number(s)

[name], Professor, [name], University of Alberta. [contact]
[name], Professor, [name], University of Alberta. [contact]
[name], Professor, [name], University of Alberta. [contact]
[name], Associate Professor, [name], University of Alberta. Tel: [name]
[name], Professor, [name], University of Alberta. [contact]

Name, title and address of qualified physician who is responsible for trial-site related medical decisions

[name], Associate Professor, Pulmonary Medicine, [name],
University of Alberta
[contact]

Trial site location and contact

Location: [name], University of Alberta, Edmonton, AB
[contact]
Physical therapist: [name]

Study Summary

Title	Can brief exposure to hyperoxia improve function after chronic spinal cord injury?
Short Title	N/A
Protocol Number	Pro00061817, Version 13
Phase	Proof-of-principle study
Methodology	Prospective, double-blind, randomized crossover design
Study Duration	Projected end date March 31, 2026
Study Center(s)	Single centre
Objectives	Determine if breathing an increased proportion of oxygen above the concentration in normal room air results in changes in the sensory and motor function in people with severe spinal cord injury (SCI).
Number of Subjects	35 (25 with spinal cord injury, 10 uninjured controls)
Diagnosis and Main Inclusion Criteria	Chronic and subacute, traumatic spinal cord injury; uninjured healthy controls for ensuring experimental protocol without using oxygen

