1.2 Preclinical Data

An abstract from the preclinical trial in rodents is included below. This study details the mechanisms underlying chronic hypoxia in the spinal cord distal to a complete spinal cord transection in a rodent model, and how brief exposure to breathing high levels of oxygen modifies the motor behaviour of the rodent. Because there is no way to measure the oxygenation in the human spinal cord non-invasively, we wish to determine if brief exposure to pure oxygen in a human with severe spinal cord injury modifies the sensory and motor behaviour in a way similar to that in rodents. If so, it would suggest that the human spinal cord distal to a severe spinal cord injury is also chronically hypoxic, and interferes with sensory and motor function. Ways to restore oxygenation to the spinal cord could then be pursued in future studies.

Pericytes impair capillary blood flow and motor function after chronic spinal cord injury

Yaqing Li¹, Ana M. Lucas-Osma¹, Sophie Black¹, Mischa V. Bandet², Marilee J. Stephens¹, Romana Vavrek¹, Leo Sanelli¹, Keith K. Fenrich¹, Antonio Dinarzo³, Stella Dracheva³, Ian R. Winship², Karim Fouad¹ and David J. Bennett¹

¹Neuroscience and Mental Health Institute and Faculty of Rehabilitation Medicine, University of Alberta, Canada; ²Neuroscience and Mental Health Institute and Department of Psychiatry, University of Alberta, Canada; ³Department of Genetics and Genomic Sciences, Icahn School of Medicine at Mount Sinai, New York, NY, USA

Nature Medicine (2017) 23(6):733 doi:10.1038/nm.4331¹

ABSTRACT

Blood vessels in the CNS are controlled by neuronal activity, including widespread vessel constrictions (tone) induced by brainstem neurons that release the monoamines serotonin and noradrenaline, and local vessel dilation mediated by glutamatergic neuron activity. We examine how vessel tone adapts to the loss of these monoamines after spinal cord injury (SCI) in rats. We find that, months after SCI, the cord below the injury is in a chronic state of hypoxia, produced by a paradoxical excess activity in monoamine receptors (5-HT1), despite the absence of monoamines. These receptors activate pericytes that locally constrict capillaries, reducing blood flow to ischemic levels. The paradoxical receptor activity results from trace amines (tryptamine) produced by pericytes that ectopically express the enzyme aromatic-L-amino-acid-decarboxylase (AADC),

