1.6 Population

Subacute or chronic (≥ 3 months post-injury), traumatic spinal cord injury. See inclusion and exclusion criteria (Sections 4.1 and 4.2, respectively, below).

A small number of uninjured participants will be included to test the experimental set-up using compressed air only. These participants will not be included in the testing of the experimental agents, but rather are used to ensure that the protocol runs smoothly prior to testing participants with spinal cord injury.

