Uninjured participants (n=10) will be included to test the study protocol for reflexes and von Frey hairs, but using compressed air only. This is to ensure the smooth running of experiments for the participants with spinal cord injury, and to provide reliability information on our testing procedures. Four experiments will be included to test the von Frey hairs and the reflexes in separate experiments, each repeated once to examine reliability of the testing (see Figure 2).

[figure not shown]

Figure 2. Experimental design for uninjured participants. Four experiments are planned for each participant. Only compressed air will be used in these experiments. Von Frey Hairs will be used to test sensation on 2 separate occasions, and reflexes will be used in the other 2 occasions.

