3.1 Primary Study Endpoints/Secondary Endpoints

The primary endpoint is the skin sensation as quantified by von Frey Hairs at specific skin locations above and below the level of injury. The exact skin location will vary, since different participants will have different levels of injury. The secondary endpoint is the reflex excitability as measured by surface electromyography (EMG) in the leg muscles, and induced by electrical stimulation of the surface of the skin on the foot arch.

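### Does Section 5's aim of studying oxygen in people without spinal cord injury, when the uninjured group breathes only air, undermine the trial or its reflex endpoint?

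*Protocol*

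**What the plan says.** Section 5 (Assessment of Efficacy) describes the experiment as one "to determine how high oxygen, delivered for a short period, affects people with and without spinal cord injury", and adds that if the effect resembles that in animals, "then new studies will be designed in the future to explore ways to improve oxygenation in people with spinal cord injury".

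The uninjured group is described differently elsewhere. The Study Summary lists "uninjured healthy controls for ensuring experimental protocol without using oxygen". Section 1.6 says "These participants will not be included in the testing of the experimental agents". Section 3 has these 10 people test the reflex and von Frey procedures "but using compressed air only", to rehearse the set-up and provide reliability data. The objective in Section 2 concerns people with spinal cord injury (SCI) only.

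On interpretation, Section 1.2 asks whether brief oxygen "modifies the sensory and motor behaviour in a way similar to that in rodents"; if it does, "it would suggest that the human spinal cord distal to a severe spinal cord injury is also chronically hypoxic". Under Section 3.1 the primary endpoint is skin sensation at sites above and below the injury, and the secondary endpoint is "reflex excitability as measured by surface electromyography (EMG) in the leg muscles", evoked by stimulation at the foot arch. Section 4.1 admits injury levels C5 to T10. Section 7.2 compares the measures before and after exposure with the room-air condition.

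**The concern.** Two things look wrong. First, Section 5 states an aim that the design cannot deliver: with no oxygen given to uninjured people, nothing can be learned about oxygen in people without SCI, and no analysis plan can supply data that are never collected.

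Second, the same absence seems to weaken the reflex endpoint. With injuries between C5 and T10, every leg reflex lies below the lesion. Room air controls for mask, flow, time and expectation. It does not control for an effect that oxygen might have on reflexes in any cord, hypoxic or not. If such an effect existed, it could be taken for relief of hypoxia and help to justify further oxygenation studies.

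**Working it through.** The protocol gives no effect size or power calculation, so the check is a count of planned sessions followed by a comparison of sections.

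**Inputs.** 25 participants with SCI and 10 uninjured (Study Summary). Four sessions each (Sections 3 and 3.5). For SCI, two oxygen days and two air days (Section 4.4), with von Frey hairs and reflexes on separate days within each phase (Section 3). For uninjured participants, two von Frey and two reflex sessions, all on air (Section 3). Attrition 10% to 15% (Section 4.3). The Study Summary speaks of two experimental days; the count follows the four-session description in the body of the protocol.

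**Sessions = participants × sessions per person.**

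| Group | All sessions | On oxygen | Reflex, oxygen | Reflex, air |
|---|---|---|---|---|
| Uninjured | 10 × 4 = 40 | 0 | 0 | 10 × 2 = 20 |
| SCI | 25 × 4 = 100 | 25 × 2 = 50 | 25 × 1 = 25 | 25 × 1 = 25 |

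After attrition, 25 × 0.85 = 21.25 to 25 × 0.90 = 22.5, so about 21 to 22 reflex pairs remain.

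**What the count shows.** The uninjured oxygen cell is empty, so the contradiction in Section 5 is real. The reflex endpoint nevertheless has its oxygen-versus-air contrast, randomized in order and made within the same people. What is absent is narrower: an oxygen reflex recording from cord that is not below an injury.

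**Does any stated aim need that recording?**

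- Section 2 asks whether oxygen changes sensory and motor function in people with SCI. The crossover answers this.
- Section 5.1 wants to show short-term motor and sensory changes below the injury. Leg reflexes under oxygen and air answer this too.
- Section 1.2 carries the hypoxia inference. It is conditional on a rodent-like change in sensory and motor behaviour, and its verb is only to suggest. A reflex change alone does not meet that condition. The sensory half has above-injury skin as a reference, and the roughly 20-minute effect in rats (Section 1.7) can be set against the 30 minutes recorded after exposure (Section 3), as a partial check on likeness.
- Sections 2, 3.1 and 7.2 make no claim about hypoxia.

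**Can the risk be sized?** Only by assumption. Suppose oxygen had a general reflex effect of 0.2, 0.4 or 0.6 SD of the paired difference. A two-sided paired t test at 0.05 with 22 pairs (noncentrality = effect × √22, 21 degrees of freedom) would detect it with probability 15%, 43% or 77%. These are ordinary power values for effects that the protocol does not give. They are not false-positive rates: a real oxygen effect on reflexes, once detected, is a correct answer to Section 2.

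**The case for a change.** The strongest case for a change is that the design, and not just the wording, leaves the reflex result open to two readings. Reflexes are the only motor outcome described, all recordings are below the injury, and deleting two words from Section 5 would not alter this. Section 5 also makes a similar effect to that in animals the reason for new studies. A sentence in Sections 1.2 and 5 limiting the reflex claim, and one in Section 3.1 naming above-injury skin as the reference, would cost no visits or measurements.

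The factual part stands: a reflex difference shows an oxygen effect in people with SCI and does not by itself separate relief of hypoxia from a general action of oxygen. The proposed sentences would gain little. Section 3.1 already measures skin above and below the injury, and how those sites are contrasted is ordinarily left to a statistical analysis plan. Section 1.2 already hedges and explains that cord oxygenation cannot be measured non-invasively in humans. Resting the inference on skin alone would drop the motor half of the Section 1.2 condition in favour of an imperfect reference: another body site, and sensation only. The consequence named in Section 5 is more research, not a treatment decision.

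**Conclusion.** No change to the plan follows. The Section 5 phrase is a clerical slip: it conflicts with the Study Summary and Sections 1.6, 2 and 3, which agree with one another, and any reader reconciles it by taking the sentence as confined to people with SCI. Nothing that is randomized, measured or compared depends on it.

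The reflex limitation is real but modest. It concerns a secondary endpoint in a self-described pilot. The oxygen-versus-air comparison in SCI is intact at 25 planned pairs, and the missing reference affects only a hedged inference that already requires sensory and motor change together. One sentence of interpretation when results are reported is enough.

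This rests on two readings: that Section 2 is the governing objective, and that the Section 1.2 condition means sensory and motor behaviour jointly. If the sponsor did intend to learn about oxygen in uninjured people, the conclusion would differ, but every operational description of that group says otherwise.

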5.1 Efficacy Parameters

Not applicable. The study is a proof-of-principle study that the high oxygen results in motor and sensory changes below the level the spinal cord injury in the short term. It is not meant to be a therapeutic agent.

5.2 Method and Timing

N/A

6 Assessment of Safety

6.2 Method and Timing

Participants will be instrumented with a non-invasive heart rate (HR) and tissue oxygen saturation monitor, clipped to the finger (Pulsox-300). HR will be constantly monitored through the experiment, including 30 min after the termination of the exposure. We expect HR could decrease slightly (~10 beats/min) (Waring et al 2003) during exposure. If these changes exceed 10 bpm during the intervention exposure, the intervention will be stopped. The participants will be monitored for 30 min after the exposure only, because there are no known subsequent effects from the short, 2-min exposure to oxygen. To ensure that there are no lingering effects, they will be contacted by phone by a physical therapist the following day to check for any issues. The phone check will be done for exposure to both oxygen and compressed air to ensure blinding.

6.3 Adverse Event Reporting

We will comply with HREB requirements to report any adverse events. The event will be reported in writing to the HREB, using the approved Local Serious Adverse Event Report form. Further, all serious unexpected adverse drug reactions (SUSARs) will be reported in writing to Health Canada.

6.4 Definitions

Unanticipated events are any events during the exposure or through the 30 min following the exposure that exceed the HR changes described above or other health issues.

Serious events are any events during the same period of time (i.e., exposure to oxygen and 30 min period following exposure) that led to the need to seek immediate medical attention at a hospital emergency and requires inpatient hospitalization.

Related events will be defined as events that occurred during or after exposure (within 30 min) to the agent (99% oxygen) which were not present prior to exposure.

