7.4 Termination Criteria

If serious adverse events (defined in 6.4) related to the exposure to high oxygen occurs in a participant, the study will be re-evaluated, and termination of the study considered.

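### Section 6.4 defines a serious event so narrowly that a death before admission, or an admission for an event starting after 30 minutes, does not meet the section 7.4 re-evaluation trigger

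*Protocol*

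**What the plan says.** Section 7.4 sets the condition for looking again at the whole study: "If serious adverse events (defined in 6.4) related to the exposure to high oxygen occurs in a participant". The consequence it attaches to that condition is: "the study will be re-evaluated, and termination of the study considered". The reference in brackets makes section 6.4 the controlling definition.

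Section 6.4 gives three categories, all tied to the same period:

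- **Unanticipated:** anything that happens while the gas is being given, or "through the 30 min following the exposure that exceed the HR changes described above or other health issues".
- **Serious:** the period is fixed first, by "Serious events are any events during the same period of time (i.e., exposure to oxygen and 30 min period following exposure"). An event inside that period must, in addition, be one "that led to the need to seek immediate medical attention at a hospital emergency and requires inpatient hospitalization".
- **Related:** "Related events will be defined as events that occurred during or after exposure (within 30 min) to the agent (99% oxygen"), provided that they were absent beforehand.

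Section 6.2 limits monitoring to 30 minutes "because there are no known subsequent effects from the short, 2-min exposure to oxygen". It then adds a further check on participants: "they will be contacted by phone by a physical therapist the following day to check for any issues". That call is made after both gases.

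**The concern.** A trigger for re-evaluating a study should at least be met by the gravest outcomes. Here it depends on a definition that requires emergency attention and inpatient admission together, does not mention death, and stops 30 minutes after the exposure. The protocol also schedules a safety contact on the following day, but 6.4 has no category for an event that begins after 30 minutes and comes to light at that contact.

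At stake is whether the protocol itself obliges the team to re-evaluate after such an event, or leaves this to their discretion. Section 1.5 commits the team to the protocol as approved, so the wording of the trigger matters.

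**Working it through.** No sample size, event rate or error rate is involved, so the check is one of logic.

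**The rule, assembled from 6.4 and 7.4**

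- Serious = (arises during exposure or within 30 min after) AND (needs hospital emergency attention) AND (requires inpatient hospitalization).
- Related = (arises during or within 30 min after oxygen) AND (absent before exposure).
- The 7.4 trigger = serious AND related.

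**The window.** The exposure lasts 2 min (section 3.4) and the period after it is 30 min (section 6.4), so the window is 2 + 30 = 32 min per session. The call in 6.2 comes the following day.

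**Cases put through the rule, each after oxygen and with nothing present beforehand**

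| Case | Serious? | Related? | 7.4 met? |
|---|---|---|---|
| A. Starts in window, emergency care, then admission | Yes | Yes | Yes |
| B. Starts in window, death before admission | No: no admission | Yes | No |
| C. Starts in window, grave, treated in emergency without admission | No: no admission | Yes | No |
| D. Starts after 30 min, admitted, found at the next-day call | No: outside window | No: outside window | No |
| E. Starts in window, admitted, first reported at the call | Yes, if emergency care was also needed | Yes | Yes |

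Cases B and C still count as unanticipated, through the reference to other health issues. Case D fits none of the three categories. Case E shows that the limit is on when the event arises, not on when it is reported or when admission takes place.

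**Does reading the conjunction as *or* help?** It would bring in case C, and case B in so far as emergency attention was needed. It does nothing for case D, which fails on timing. Widening the window for serious events alone would not help D either, because related has the same 30-minute limit.

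**Do other sections close the gap?**

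- Section 3 has the team consider termination if symptoms of early oxygen toxicity emerge. It needs no admission and states no 30-minute limit, so it catches any of these events that show as such symptoms, but not the others.
- Section 6.3 concerns reporting to the ethics board and Health Canada. Section 6.5 concerns daily follow-up and notice to the board. Neither requires re-evaluation of the study.
- Section 9 declares general GCP compliance. It does not replace the explicit reference from 7.4 to 6.4.

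**The case against.** **Section 7.4 does not say *only*.** It states a condition that is sufficient for re-evaluation and bars no other review. A reader might infer that the protocol forbids or rules out review after a death before admission. The text does not support that: it is silent on such events, and the team remains free to act. This objection stands and limits the point to what is mandatory.

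**Section 3 covers part of the ground.** Its toxicity trigger starts at mild symptoms, and section 1.3 describes early signs broadly, including an abnormal rise in blood pressure. Many in-window events treated without admission would be caught there. This also stands. What is left of cases B and C is a death or grave event without such symptoms.

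**A fatal event could be said to have required hospitalization even if admission never took place.** That is a possible reading, but a trigger of this kind should not depend on it when naming death would settle the matter.

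**The 30-minute period has a stated reason.** Section 6.2 gives it, and sections 1.4, 3 and 3.6 place toxicity at hours of exposure. A reader might infer that the monitoring period is unjustified, or that the call contradicts it. Neither follows: the call is an added check. The reason explains how long participants are watched; it does not explain why an event found at the call should have no classification.

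**Late events are not lost.** Sections 6.3 and 6.5 are not limited to 32 minutes, so an inference that these events go unreported would be wrong.

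**Lengthening the window has a cost.** Related is defined by timing and prior absence alone. Carrying that test to the next day would label every new event after oxygen as related, including coincidental ones. This objection stands and shapes the fix.

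**Conclusion.** The concern holds in a limited form. Under the literal wording of 6.4, a death before admission, or a grave in-window event treated without admission and without the toxicity symptoms of section 3, does not meet the 7.4 trigger. An event that starts after 30 minutes is outside every 6.4 category, even if it leads to admission. The gap is in the formal classification and the mandatory trigger, not in all reporting and not in the team's freedom to review.

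The conclusion rests on two assumptions: that the two hospital conditions are read as joint, as written, and that 7.4's reference to 6.4 is binding. The late-onset part does not depend on the first.

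The documents give no event rate, so no number of missed events can be computed, and a count of planned oxygen sessions would not measure the defect. No efficacy endpoint or estimate changes. The correction is still worth making, because a re-evaluation rule should not need interpretation to cover a death.

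**What to change.** 1. In section 6.4, state the seriousness criteria as alternatives, joined by *or*, and include death. Section 7.4 then refers to the corrected definition without further change on this point.
2. Reconcile sections 6.2, 6.4 and 7.4 so that a serious event found at the next-day call can be classified and considered under 7.4.
3. Do not simply lengthen the time-only test for related. For an event that starts after 30 minutes, let the study's medical expert judge relatedness.

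The cost is protocol wording, submitted as an amendment. The call is already planned after both gases, so no contact or procedure is added. The downside is that a few more events, some coincidental, will need classification and a judgement of relatedness.
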